 - Ocular foreign body (e.g. metal shavings)
 - Embedded shrapnel fragments
 - Central nervous system aneurysm clips
 - Implanted neural stimulator
 - Medical infusion pumps
 - Any implanted device that is incompatible with MRI.

- (b) Is not likely to tolerate an MRI scan. Examples of medical conditions that would make it difficult to undergo MRI include severe anxiety (nervousness) or hyperactivity which make it hard for your child to lay flat for the study.
- (c) Requires sedation for MRI studies.
- (d) Has a condition that makes entry into the scanner difficult (e.g. weight over 550 lbs, claustrophobia, etc.).
- (e) Has severe back-pain or motion disorders that make it hard for a child to lie on his/her back within the MRI scanner and hold still for the scan.

4. Study Design and Methods

a. Study Overview:

- i. **Trial Design:** We will carry out a parallel group randomized controlled trial that compares child carbohydrate metabolism and cognitive function during 5 days of sedentary after-school activities versus after-school activities with structured interruptions provided by walking for 3 minutes on a treadmill every 30 minutes at a moderate activity rate selected according to each participants' level of fitness. A final 6th day will compare results between groups from an oral glucose tolerance test conducted in the fasted state. Subjects will be randomized to one of two conditions:
 - (a) **Study Intervention: Interrupted sedentary behavior.** This test condition will consist of 6 consecutive daily after-school /afternoon visits for a three-hour experimental session. The first five sessions will be performed mid-afternoon (Monday – Friday, after school or late afternoon); the 6th will be in the morning (Saturday, approximately 8am). Each session will consist of prompted 3-minute moderate-intensity walking bouts performed on a treadmill every 30 minutes for 3 hours. There will be a total of 6 walking bouts (18 minutes total) each day. 'Moderate-intensity walking' speed and grade will be selected to achieve 80% of the heart rate achieved at the ventilatory threshold as determined during a $\dot{V}O_{2max}$ test.

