- ii. Protocol review and signing of consent and assent forms.** Parents/guardian(s) and participants will review the consent and assent forms with study personnel designated to do so by the PI. All study procedures will be discussed, and study risks and benefits explained. Communication of this information and of the participant's consent will be documented in the medical record before any study procedures, including other screening procedures, are done. All participants will be informed of their right to withdraw from the study at any point. Participants will be informed of compensation. Parent/guardian(s) and participants will be given signed copies of the consent and assent form for their records.
- iii. Complete medical history and physical exam** will be conducted by a trained practitioner. The exam will include Tanner pubertal staging. Waist and hip circumference (cm) will be measured in triplicate by nutrition staff (see below).
- iv. Practice measures.** Participants will be oriented to all procedures that will occur throughout the screening visit day (with the assistance of Child Life services) to reduce any anxiety.
- v. Fasting blood draw.** A fasting blood sample will be drawn to screen for exclusionary conditions and determine metabolic, hematologic, renal, and hepatic function including: acute care panel, insulin, c-peptide, free fatty acids, triglycerides, hemoglobin, creatinine, thyroid function tests (including anti-thyroid antibody panel), mineral, and hepatic panels, thyroid function tests (TSH and Free Thyroxine), C-reactive protein, Hemoglobin A1C, complete blood count, serum beta-human chorionic gonadotropin or urine pregnancy test, and serum and plasma samples to be saved for future research. ELA Max cream will be applied to numb the blood draw site.
- vi. Socioeconomic status (SES).** A demographics questionnaire that assesses race/ethnicity and parent/guardian education level and income will be completed by the parent/guardian so that the Hollingshead two-factor index of social position can be calculated.¹⁴⁵ See Appendix G.

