- understand will be explained. The scale measures acute (state) anxiety and longer-term (trait) anxiety. It asks the child to rate 20 statements from ‘hardly every true’ to ‘often true’ and takes approximately 15 minutes to complete. The scale has been validated in 1551 children ages 6-14 years. Subjects will complete the STAIC through the NIH Clinical Trials Survey System.
- xii. Physical Activity Evaluation.** To determine the average amount of moderate-to-vigorous physical activity each participant has engaged in within the previous week, children will be asked two items from the International Physical Activity Questionnaire (IPAQ) screening form (See Appendix G).¹⁵⁶ This information will be used to:
 - a. Determine caloric requirements for standardized meal calculation
 - b. Stratify participants for randomization purposes.
 - xiii. Dietary Evaluation & Metabolic Diet Education.** Participants will be interviewed by and receive education instruction from the nutrition staff. This will allow us to obtain each participant’s meal preferences and provide metabolic diet education (i.e. goals of the metabolic diet throughout the study period) to improve adherence. Additionally, waist and hip measurements will be obtained in triplicate.
 - xiv. Electrocardiogram (EKG).** All children will undergo an EKG. If the EKG or physical examination suggests possible concerns in cardiovascular function, echocardiography &/or formal cardiology consultation will be obtained before the participant performs the maximal exercise test.
 - xv. Dual-energy x-ray absorptiometry (DXA) scan.** As part of a whole-body composition and bone mineral density assessment, DXA scan will be performed to identify lean and fat mass. DXA involves passing a collimated X-ray beam of 40 and 70 KeV through the subject and collecting the X-rays that pass through the patient with a standard X-ray detector. Because the delivery and attenuation of the X-rays are measured separately for the two principal energies, the procedure allows the differentiation of substances in their path if the attenuation coefficients of these substances are known. The manufacturer specifies that the array beam delivers an effective dose of 0.003mrem total body irradiation. Participants will undergo DXA scans in the Metabolic Clinical Research Unit (MCRU) using the Lunar iDXA (GE

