- b. **Secondary outcomes** are glucose iAUC obtained during the oral glucose tolerance test; mean iAUC as obtained from 24hr- continuous glucose monitoring, and Mean Amplitude Glycemic Excursion (MAGE) as obtained from 24hr- continuous glucose monitoring. Tertiary outcomes are cognitive function (working memory, inhibition, attention, and processing speed), mood, anxiety, daily physical activity (steps counts/day), and dietary intake at the final test meal. Improved circulating glucose values as demonstrated by lower glucose iAUC would directly support our primary insulin outcome and would be clinically relevant as this result would indicate improved metabolism. Additionally, MAGE has been demonstrated to be associated with metabolic control such that elevated MAGE is associated with worsening cardiometabolic outcomes in individuals with diabetes.¹⁶⁷

The executive function, mood and anxiety outcomes are being collected for independent objectives. This group of measures is an important objective to provide information that will be necessary to know for feasibility of this intervention. This intervention is poised to community application such as school class rooms. Therefore, it is important to understand if executive function is adversely affected by the intervention as this would limit its feasibility for implementation. Finally, all analyses will be performed within the subgroups of healthy weight and overweight subjects to evaluate for differential effectiveness based on weight status.

10. Statistical Analysis

- a. Analysis of data.** Prior to conducting the main model analysis, descriptive analyses will be conducted on all outcome and covariate to assess potential outliers and calculate summary statistics. If significant deviations from the assumed distribution (e.g.: normal) occur, then appropriate transformations will be applied to fulfill model assumptions. If transformations are not sufficient to meet model assumptions, then nonparametric tests will be used. Descriptive statistics will investigate correlations between variables at pre-test and post-test to assess potential confounders prior to analyses.

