The parallel study design allows for the examination of between-individual comparisons of test effects and within-individual longitudinal test effects (i.e. repeated daily CGM metrics). Significance level will be set at $\alpha = 0.05$. Covariates will include: age, sex, race/ethnicity, baseline cognitive ability (for cognitive outcomes only), baseline homeostatic model of insulin resistance (HOMA-IR), body fat mass (except for subgroup analysis by weight status), and Tanner stage. We will also evaluate for a weight status interaction (intervention x healthy weight / overweight).

The following analyses will be performed:

- i.** Participant characteristics will be summarized using means (standard deviations) and frequencies.
- ii.** Baseline (time 0) values for participant characteristics, insulin, glucose, heart rate, and blood pressure between the groups will be compared using t-tests.
- iii.** The primary analysis will be ANCOVA comparing children randomized to the two groups for insulin iAUC at the end-study oral glucose tolerance test, with age, sex, race/ethnicity, HOMA-IR, body fat mass, and Tanner stage as variables in the model. If all covariates are nonsignificant, unpaired t-tests will be reported for the differences in OGTT insulin iAUC by condition (prolonged vs interrupted sitting). Similar analyses will be used to examine glucose iAUC, 5- or 6-day average 24hr CGM iAUC and 24hr MAGE. (Subjects may only have 5 days of CGM data if a device is

accidentally removed and replaced at the next visit or subject uses a medication that interacts with glucose readings such as acetaminophen-after which 24hrs of data will be omitted from analysis). Mixed models will also be used to assess the influence of prolonged vs. interrupted sitting on insulin and glucose iAUC over the 3 hours of observation. To evaluate differences in the dependent variables at each time point, planned comparisons of model-based mean differences between each time points will be calculated. Additionally, mixed models will be used to assess condition influence on mean 24hr CGM glucose iAUC and 24hr MAGE.

- iv. ANCOVA or (as indicated above) t-tests will investigate differences in working memory, inhibition, attention, processing speed, mood, anxiety, and kcal intake between prolonged sitting and interrupted sitting at the post- test.

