- v. Mixed models will also be used to assess the influence of prolonged vs. interrupted sitting on change in cognitive function, mood and anxiety (pre-post test scores) controlled for significant covariates. Covariates to be considered include those listed above in addition to free living activity and sleep.
- vi. As a secondary analysis, all the analyses described above will be performed on the subgroups: Healthy weight and overweight subjects.
- vii. Supplemental MRS Study: Repeated measures ANOVA will investigate the change in IMCL content between baseline & pre-session (thus, evaluating for daily intervention effect) as well as immediately pre- and post-intervention session (thus, evaluating the immediate effect of intervention) by condition. ANCOVA analyses will compare the change in IMCL content by condition with age, sex, race/ethnicity, HOMA-IR, body fat mass, and Tanner stage as variables in the model.

b. Power Analysis

Based on our preliminary published data,⁶⁵ and our unpublished data in overweight youth, we expect a moderate to large (Cohen's $d = 0.8$) effect size. With an 80% power, $\alpha=0.05$, our sample size requires evaluable data from 21 in each group; with our goal of subgroup analysis within healthy weight and overweight groups, we will require 84 participants total (42 overweight and 42 healthy weight). This is supported by previously reported adult data published by Dunstan et al. who identified the mean (standard

deviation) difference between the two groups was 191.0 (334.9) pmol/L yielding a moderate to large effect size.⁴⁸ Taking into consideration more variability due to the parallel design (versus cross over designs used previously), we will randomize up to 120 participants and estimate that at most 36 children will drop-out of the study before completion. We expect at least 84 participants to complete the protocol which is our target completion based on these analyses.

11. Human Participant Protections

a. Rationale for subject selection

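### Free-living physical activity is a Hypothesis 2 outcome that Section 10 never compares between arms, and the buffet-intake model omits an available screening measure of body size or energy need

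*Combined protocol and SAP*

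**What the plan says.** **Activity as an outcome.** Hypothesis 2 in Section 2 states that activity outside the testing period will not differ between arms. Section 9.b lists among the tertiary outcomes "daily physical activity (steps counts/day), and dietary intake at the final test meal". Section 4.d.i.f has each child wear a wrist accelerometer from Day 1 to Day 6, in part to see whether out-of-session activity is altered by the intervention.

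**Activity in the analysis section.** Section 10.a.iii sets out the insulin ANCOVA and then adds: "Similar analyses will be used to examine glucose iAUC, 5- or 6-day average 24hr CGM iAUC and 24hr MAGE". In Section 10.a.iv, ANCOVA or "t-tests will investigate differences in working memory, inhibition, attention, processing speed, mood, anxiety, and kcal intake between prolonged sitting and interrupted sitting". Section 10.a.v models change in cognition, mood and anxiety, and says "Covariates to be considered include those listed above in addition to free living activity and sleep". That sentence is the only place where Section 10 mentions free-living activity.

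**Covariates for buffet intake.** The general list in Section 10.a reads "Covariates will include: age, sex, race/ethnicity, baseline cognitive ability (for cognitive outcomes only), baseline homeostatic model of insulin resistance (HOMA-IR), body fat mass", followed by Tanner stage. Section 4.c.xii gives as one use of the screening IPAQ items "Determine caloric requirements for standardized meal calculation", and Section 4.d.i.g says the calculation also uses body weight. Section 4.c.xv obtains lean and fat mass by DXA at screening. Of these, only fat mass is in the covariate list.

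**The concern.** Objective 2 asks whether interrupting sitting has unwanted effects. One plausible effect is that children who walk in the sessions move less for the rest of the day. The trial collects data to answer this, but the analysis section specifies no test, estimate or model for it. An analyst following Section 10 would finish without addressing that part of Hypothesis 2. An analyst who added the comparison later would be choosing the measure, the time window and the covariates after seeing data.

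The one role that Section 10 gives the variable makes the gap more awkward. Activity during the intervention week may be affected by the assigned arm. The plan would consider adjusting other outcomes for it without ever examining it as an outcome.

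Buffet intake is a smaller matter. Energy eaten by children aged 7 to under 12, across healthy weight and overweight, plausibly depends on body size and energy need. The trial has two such measures before randomization and uses neither in this model. What is at stake there is precision, not bias.

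**Working it through.** **1. Is activity compared anywhere in Section 10.a?**

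- Opening paragraphs: outlier checks, summary statistics and correlations for all outcomes. No arm comparison.
- Item i: summaries of participant characteristics.
- Item ii: time-0 comparison of characteristics, insulin, glucose, heart rate and blood pressure.
- Item iii: insulin iAUC, glucose iAUC, CGM iAUC and MAGE.
- Item iv: cognition, mood, anxiety and kcal intake.
- Item v: change in cognition, mood and anxiety, with activity and sleep as candidate covariates.
- Item vi: repeats the preceding analyses by weight status, so it adds no outcome.
- Item vii: intramyocellular lipid.

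No item compares activity between arms. Section 4.d places randomization after screening and Section 4.d.i.f issues the device on Day 1, so every accelerometer value is post-assignment. The only activity measure taken before randomization is the screening IPAQ. Section 4.d uses it (low, moderate, high) as a stratification factor, but it is not in the covariate list.

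**2. The window matters.** The interrupted arm walks 6 × 3 = 18 minutes a day on the treadmill by design. A whole-day step count would therefore differ between arms through the intervention itself. Hypothesis 2 concerns time outside the sessions, so the session hours must be excluded.

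**3. What the missing comparison could detect.** Section 10.b gives 21 × 2 arms × 2 weight groups = 84 completers, and 120 − 36 = 84. That is 42 per arm. Sidedness is not stated; two-sided 0.05 and 80% power are assumed here.

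- Unadjusted: (1.960 + 0.842) × √(2/42) = 0.61 SD.
- Adjusted for a baseline with correlation ρ to the outcome, multiply by √(1 − ρ²). With ρ = 0.3 this gives 0.58 SD; with ρ = 0.5 it gives 0.53 SD.

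The values of ρ are assumptions; the documents give none for IPAQ and accelerometer steps.

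**4. Buffet kcal: gain and cost of one added covariate.** Let R be the share of the variance left by the existing covariates that the new one explains. The effective sample size is 84/(1 − R).

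- R = 0.05: 84/0.95 = 88.
- R = 0.20: 84/0.80 = 105.

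The cost if the covariate explains nothing, assuming about 7 existing covariate terms, is the variance factor (n − 7 − 3)/(n − 8 − 3).

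- n = 84: 74/73 = 1.014, a loss of about 1%.
- n = 42 (one weight subgroup): 32/31 = 1.032, a loss of about 3%.

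At the low end of the range the net factor is 0.95 × 1.014 = 0.96 in the full sample and 0.95 × 1.032 = 0.98 in a subgroup. Both are still below 1. The break-even R is about 1% and 3% respectively.

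**The case against.** The case for leaving the plan alone has four parts.

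- *The intent is plain.* Hypothesis 2 and Section 4.d.i.f say what the activity data are for, and a competent analyst would run the obvious ANCOVA. This is one tertiary outcome in a pilot, missing from one list. That fairly limits the importance of the point. It does not supply the measure, time window or covariates, which the treadmill walking makes a real choice.
- *Section 10.a already allows for confounders.* Correlations are to be examined before the main models. That is data-driven selection of covariates, and it provides no comparison of activity between arms.
- *The arms are balanced by design.* Sex, age, weight status and IPAQ level are all strata. This answers a worry about bias, which is not claimed here. It does not remove the possible gain in precision from adjusting for a prognostic variable.
- *The buffet model already carries body size.* Age, sex, Tanner stage and fat mass are in it, and the calculated requirement is built from weight and IPAQ activity. This stands in part: the added information may be small, and no correlation in the documents shows otherwise.

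**Conclusion.** The activity gap is established from the text and needs no numerical assumption: a named component of Hypothesis 2 has no between-arm analysis in Section 10. With 84 completers, the comparison would detect about 0.61 SD without adjustment, assuming a two-sided 0.05 test and 80% power. The buffet suggestion is a modest improvement. Its size (84 acting like 88 to 105) rests wholly on the assumed further 5% to 20% of variance explained. Both are minor relative to the primary insulin analysis, which they do not touch.

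Three stronger readings are tempting, and the documents do not support them.

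- A reader might infer that the glucose, CGM and buffet outcomes are left unadjusted for baselines of their own that were collected. None was. On the OGTT, Section 4.a.i says "A final 6th day will compare results between groups from an oral glucose tolerance test conducted in the fasted state"; the buffet is given only on Day 6; and the glucose sensor is placed on Day 1 of the intervention. The 24-hour food recall on Day 1 is a different instrument from the buffet.
- A reader might infer that one covariate list serves every outcome. Section 10.a adds baseline cognitive ability for cognitive outcomes and drops fat mass in the weight subgroups, and item v extends the list.
- A reader might infer that screening fasting glucose and HbA1c (the latter in Section 4.c.v: "C-reactive protein, Hemoglobin A1C, complete blood count") ought to join the glucose and CGM models. Fasting glucose already enters through HOMA-IR and is restricted by eligibility to below 100 mg/dL, so a gain beyond HOMA-IR is unsupported. Two uninformative terms in a subgroup of 42 would cost (42 − 7 − 3)/(42 − 9 − 3) = 32/30, about 7% of variance, again assuming about 7 existing terms.

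**What to change.** 1. In Section 10.a.iv, add an ANCOVA comparing accelerometer step counts per day between arms, with session hours excluded and adjusted for screening IPAQ category. Report the difference with a 95% confidence interval, because the hypothesis is one of no difference. With three categories, IPAQ uses two degrees of freedom.
2. In the same item, name one pre-randomization covariate for buffet kcal: either DXA lean mass or the calculated daily energy requirement, chosen before the data are seen. This uses one degree of freedom.

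The cost is two sentences of plan text. All the variables are already collected at screening, derived from screening data, or recorded by the accelerometer, so no visit, measurement or sample size changes.

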- e. **Continuous glucose monitoring:** Beginning on day #1 of testing/intervention, a continuous glucose monitor (Libre Pro, Abbott products) will be placed on each child to record glucose trends continuously throughout their 6-day study. The Libre Pro device will be evaluated for placement, skin irritation, function, and data collection daily at each testing visit. It is expected that only 1 device will need to be placed to complete the entire 6-day study. On Day #6, the final day of testing, the Libre Pro device will be removed. Continuous glucose monitoring data will allow calculation of average daily glucose iAUC as well as mean amplitude glycemic excursion (MAGE; the arithmetic mean of all increases or decreases in glucose that exceed 1 SD of the total set of glucose values). If a device is lost/falls off between study sessions, a replacement device will be placed on the subject. If a child consumes a listed medication known to interact with glucose readings (acetaminophen, vitamin C, and aspirin), the following 24hrs of CGM data will be admitted from their analyses but the device will otherwise remain on the subject to continue collecting data throughout the remainder of their study block.
- f. **Continuous physical activity monitoring:** On day #1 of testing/intervention participants will be given a wrist accelerometer (Actigraph GT3X+) to wear continuously throughout their 6-day intervention to assess in-study as well as free-living activity, sedentary behavior, and sleep efficiency. This device will also be removed on day #6 and data will be downloaded. These data will be used to determine if physical activity outside of the test condition changes as a result of intervention. Additionally, the participant will be fitted with a hip accelerometer on test visit #6, which will be worn for the entirety of test visit #6. These monitors will provide added data to evaluate fidelity of the interventions.

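### The 5- or 6-day CGM average does not fit the sensor schedule: wear gives never six complete 24-hour windows and usually four, and counting Saturday brings in the OGTT

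*Combined protocol and SAP*

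**What the plan says.** **CGM outcome.** Section 10.a.iii plans an ANCOVA on the "5- or 6-day average 24hr CGM iAUC and 24hr MAGE". A bracketed note explains when a child would have five days: the device was accidentally removed and replaced at the next visit, or a medication interfered, after which "24hrs of data will be omitted from analysis". Six days is therefore the normal case. The same item adds that "mixed models will be used to assess condition influence on mean 24hr CGM glucose iAUC and 24hr MAGE".

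**Sensor schedule.** Section 4.d.i.e places the sensor on day 1 and removes it on day 6. It defines MAGE from rises and falls that "exceed 1 SD of the total set of glucose values". Section 4.a.i puts days 1 to 5 on Monday to Friday, mid- to late afternoon, and day 6 on Saturday at about 08:00. Section 4.a.ii gives the last visit about 5 hours. The Test Day #6 list puts sensor removal after the OGTT and the buffet meal.

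**MRS arm.** On day 4 or 5 the sensor comes off before a scan at about 12pm, and a new one goes on after a scan at about 4pm. Up to 75 children may join.

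**Baseline.** Section 10.a.ii states: "Baseline (time 0) values for participant characteristics, insulin, glucose, heart rate, and blood pressure between the groups will be compared using t-tests". The covariate list in 10.a has "baseline homeostatic model of insulin resistance (HOMA-IR"; the primary model is fitted "with age, sex, race/ethnicity, HOMA-IR, body fat mass, and Tanner stage as variables in the model". Neither names the blood sample.

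**The concern.** A sensor worn from Monday afternoon to Saturday midday covers parts of six dates but does not hold six 24-hour periods. The plan gives no rule for the part-days, so two analysts could average different hours and both claim to follow it. The choice matters because the Saturday readings are unlike the others: they contain a fasting glucose load and then a buffet. Counting Saturday as a day would make the CGM result partly repeat the OGTT glucose result, which Section 9 lists as a separate secondary outcome.

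A smaller matter sits beside it. Time 0, applied to insulin and glucose, can be read as the day-6 OGTT sample, which is drawn after five sessions of the assigned condition. A value from that sample is not a baseline for comparing arms.

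**Working it through.** **1. Wear time.** Inputs: Monday placement at hour *s*; removal at about 08:00 + 5 h = 13:00 on Saturday. The protocol gives no clock time for placement, so 13:00 to 17:00 is assumed. The 13:00 end comes from the MRS section: a 3-hour session that ends at about 4pm starts at about 1pm.

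Wear = (24 − *s*) + 4 × 24 + 13. Complete windows counted from placement = whole part of wear/24.

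| Placement | Wear (h) | Complete windows |
|---|---|---|
| 13:00 | 120 | 5 |
| 14:00 | 119 | 4 |
| 15:00 | 118 | 4 |
| 16:00 | 117 | 4 |
| 17:00 | 116 | 4 |

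Six windows need 6 × 24 = 144 h. Widening the inputs to placement 12:00 to 17:00 and removal 12:00 to 14:00 gives 115 to 122 h, so the plan's figure of six is not reproduced under any of these. A fifth window appears only when placement is no later in the day than removal, and it then runs to Saturday's removal time and contains the OGTT.

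**2. Calendar days.** Midnight to midnight, Tuesday, Wednesday, Thursday and Friday are complete in every case: four days. Monday holds 24 − 17 = 7 h to 24 − 13 = 11 h. Saturday holds about 13 h, of which about 5 h (08:00 to 13:00) are the test visit.

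**3. Weight of the part-days in a six-day mean.** Weight: 2/6 = 33%. Share of hours: (11 + 13)/120 = 20.0% for 13:00 placement, (7 + 13)/116 = 17.2% for 17:00 placement.

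**4. Effect on the MAGE threshold (illustration only).** Suppose the SD is pooled over all wear, as the definition in 4.d.i.e reads. Let *w* be the share of readings from the Saturday visit (5/120 to 5/116), *s* the SD of the other readings, *t* the SD within the visit, and *D* the difference in means. Then

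SD ratio = √[(1 − *w*)*s*² + *w t*² + *w*(1 − *w*)*D*²] / *s*.

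None of *s*, *t* or *D* is in the documents. With *s* = 15, *D* = 30 and *t* = 20 to 25 mg/dL the ratio is 1.09 to 1.11. With *s* = 12 to 18 and *D* = 15 to 45 it is 1.02 to 1.31. A higher SD raises the threshold on every day, so ordinary excursions can drop out of MAGE. If the SD were taken day by day, only Saturday's MAGE would be affected.

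**5. MRS children.** The gap runs from before about 12:00 to after a scan that starts at about 16:00. On day 4 it breaks Thursday; on day 5 it breaks Friday. Either way 4 − 1 = 3 complete days remain. This can apply to up to 75 of 120 randomised children (62.5%), and 10.a.iii does not list it as a reason for fewer days.

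**6. Medication omission.** A 24-hour omission that starts during Tuesday, Wednesday or Thursday touches two of the four days. One that starts on Monday after placement, or on Friday, touches one. So two or three complete days remain.

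**7. Baseline sample.** Two blood collections are scheduled: the fasting draw at screening (4.c.v), before randomisation, which includes insulin; and the day-6 OGTT series, the only one with a sample labelled time 0. The label is also used on days 1 and 5, but there for cognitive tests and questionnaires, not blood.

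**The case against.** **Days may simply mean study days, since the protocol speaks of a 6-day study.** That is a fair reading of the intent. It does not settle the calculation, because the outcome is built from 24-hour metrics and only four dates have 24 hours. A mean that includes part-days can be computed, but the plan gives no rule for it.

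**Four is not a ceiling.** This stands. Visit times are approximate, efforts will be made to schedule visits in school holidays, and an early start can give a fifth window.

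**Fewer windows might be taken to mean lost precision or power.** The documents do not support that. Six windows were never available, so nothing is lost; only the description is wrong.

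**Section 4.d.i.e seems to keep the readings that 10.a.iii drops.** It says "the following 24hrs of CGM data will be admitted from their analyses". This is evidently a slip for omitted, as 10.a.iii confirms, and needs only correction.

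**A reader might infer that the primary ANCOVA adjusts for a post-randomisation HOMA-IR.** The covariate list says baseline, and the shorter label in the primary model reads naturally as the same variable. No section proposes a day-6 HOMA-IR. What stands is that the source sample is unnamed and the time 0 label points to the wrong visit.

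**A reader might infer that the primary OGTT is invalid because the assigned condition runs during it.** It is not: Hypothesis 1a asks only for lower iAUC during that test, and Test Day #6 states the arrangement openly.

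**Conclusion.** The point holds for the CGM outcomes. On the stated schedule the normal case of six 24-hour days cannot occur. Wear of about 116 to 120 h usually gives four complete windows, five only with placement by about 13:00, and four complete calendar days in every case (three for MRS children). Counting the part-days gives them 33% of the mean on 17% to 20% of the hours and lets the OGTT and buffet into iAUC and MAGE. These figures rest on the approximate visit times and the assumed placement hours; the size of any MAGE threshold shift rests wholly on assumed glucose values.

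The baseline matter is a clarification, not a demonstrated bias.

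On the OGTT, one note is enough. The primary contrast shows an effect under the condition on day 6 and does not separate a same-session effect from carry-over. The précis calls the test post-condition, which should be reconciled with the Test Day #6 procedures.

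Overall weight is minor to moderate. Section 9 classes both CGM measures as secondary, and nothing here prevents the trial from detecting an effect on its primary outcome.

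**What to change.** 1. In 10.a.iii, define the CGM outcomes as the mean over available complete calendar days, Tuesday to Friday: up to four, and three for MRS children.
2. Exclude readings from the start of the day-6 OGTT onward from iAUC, MAGE and the SD that sets the MAGE threshold.
3. List the MRS sensor change as a planned gap. Handle days lost to it, or to a medication omission, through the mixed model already named for the daily CGM measures. State that a day touched by an omission is not complete, and correct the wording slip in 4.d.i.e.
4. In 10.a.ii and 10.a.iii, name the screening fasting draw as the source of baseline insulin, glucose and HOMA-IR.
5. Reconcile the précis with the Test Day #6 text, and state that the primary contrast is the effect under the condition on day 6.

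Midnight boundaries are preferable to windows cut at 08:00. Children fast before Saturday's visit, so a Friday-to-Saturday window ending at 08:00 could hold no breakfast while the others do.

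**Cost.** Wording only, on data already being collected. The Monday session and the part of Friday night after midnight fall outside the averaged days, and the stated day count is lower. Screening values can be up to 90 days older than the start of the test week, so they may explain less of the variation.
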